2.2.2. Number of Subjects

It is anticipated that approximately 17,476 adults, 50 years of age and above, will be enrolled globally to accumulate 66 first primary CDI cases (meeting case definition 1, [Section 3.4.1](#)). As this is an event-driven and group-sequential (GS) study, the final enrollment number may vary depending on the incidence rate of the primary endpoint, true underlying VE, and potential to stop early for efficacy or futility. The number of subjects enrolled in each country and at each site will vary based on enrollment capabilities.

To achieve a broad representation of age groups among those 50 years of age and older, and achieve an adequate rate of CDI, the numbers of subjects intended to be enrolled in each of 4 age groups are shown in Table 2.

Table 2. Intended Number of Subjects Included in the Study, by Age Group

Category	Subcategory	Minimum Number for Inclusion	Maximum Number for Inclusion
Age	50-59 years	800 subjects	1600 subjects
	60-69 years	1600 subjects	Not limited
	70-79 years	1600 subjects	Not limited
	≥80 years	400 subjects	Not limited

On monitoring the pooled primary CDI event rates in different age groups, inclusion criteria subgroups, Charlson Comorbidity Index (CCI) subgroups, and subgroups based on other baseline factors ([Table 3](#)), once the specified minimum numbers in each age group have been achieved, if a substantially higher pooled CDI event rate is observed in some subgroups, the intention may be to stop enrollment in lower-risk subgroups and complete enrollment with the higher-risk subgroups thereafter. This is mainly to help to achieve the targeted total number of first primary cases in a timely manner.

Table 3. Number of Subjects in Other Categories to Be Monitored for Inclusion in the Study

Category	Subcategory
Charlson Comorbidity Index	0
	1
	2
	3
	≥4
Subject inclusion criterion 4	At least 1 inpatient hospitalization ≥2 nights' duration in the previous 12 months.
	At least 2 emergency room visits in the previous 12 months.
	At least 10 outpatient visits (primary and/or secondary care visits but excluding pharmacy and mental health visits) in the previous 12 months.
	Residence in a skilled nursing facility (a residential institution that provides professional nursing care and rehabilitation services, usually following discharge from the hospital).
	Residence in a nursing home (a residential institution that provides assistance with activities of daily living).
	Inpatient hospitalization ≥2 nights' duration scheduled ≥37 days after randomization.
	Received systemic (ie, oral or injected) antibiotics at any time in the previous 12 weeks.

Subjects withdrawn from the study after randomization will not be replaced, regardless of the reason for withdrawal.

2.2.3. Schedule of Activities

Table 4. Schedule of Activities

Visit ID	Visit 1	Visit 2	Visit 3	Visit 4	Visit 5	Visit 6	Annual Retention Visit	Visit 7	At Time of Potential CDI Case
Visit Description	Month 0 (Vax 1)	Month 1 (Vax 2)	Month 2	Month 6 (Vax 3)	Month 7	Month 12		End of Study	
Visit Window (Days)	1	28-42 Days After Visit 1	28-42 Days After Visit 2	140-168 Days After Visit 2	28-42 Days After Visit 4	165-195 Days After Visit 4	Every 280-392 Days After Visit 5 ^a	Not Applicable	
Informed consent ^b	X						X ^c		
Demography ^b	X								
Clinical assessment, including medical history ^b	X								
Record nonstudy vaccinations ^d	X	X	X	X	X				
Record specified concomitant medications									X
Measure and record height and weight ^b	X								
Oral temperature ^b	X	X		X					
Urine pregnancy test (females of childbearing potential) ^b	X	X		X					
Discuss contraceptive use ^d	X	X	X	X					
Confirm eligibility ^d	X	X	X	X					
Review temporary delay criteria ^b	X	X		X					
Randomization ^b	X								
Blood draw for immunogenicity assessment ^d	X		X		X				X ^c
Vaccination	X	X		X					
Postvaccination observation (at least 30 minutes) and AE assessment	X	X		X					

Table 4. Schedule of Activities

Visit ID	Visit 1	Visit 2	Visit 3	Visit 4	Visit 5	Visit 6	Annual Retention Visit	Visit 7	At Time of Potential CDI Case
Visit Description	Month 0 (Vax 1)	Month 1 (Vax 2)	Month 2	Month 6 (Vax 3)	Month 7	Month 12		End of Study	
Visit Window (Days)	1	28-42 Days After Visit 1	28-42 Days After Visit 2	140-168 Days After Visit 2	28-42 Days After Visit 4	165-195 Days After Visit 4	Every 280-392 Days After Visit 5 ^a	Not Applicable	
Review stool sample collection and shipping instructions with the subject and ensure understanding	X	X	X	X	X	X	X		
Issue or send a stool collection kit and shipping box, and provide instructions on their use, as required	X	X	X	X	X	X	X		
Issue measuring device and thermometer and provide instructions on their use, as required	X	X		X					
Review subject communication methods (including for e-diary completion), assist the subject with downloading the app, or issue provisioned device, if required	X	X	X	X	X	X	X		
Record AEs	X	X	X	X	X ^f				X ^f
Record SAEs	X	X	X	X	X	X			
Capture major protocol violations		X	X	X	X	X	X	X	X
Telephone contact visit						X ^g		X	X
Electronic reminders		←						→	
Telephone contact for subjects unresponsive to electronic reminders		←						→	
Provision of stool sample									X
Completion of diarrheal episode questionnaire									X

Table 4. Schedule of Activities

Visit ID	Visit 1	Visit 2	Visit 3	Visit 4	Visit 5	Visit 6	Annual Retention Visit	Visit 7	At Time of Potential CDI Case
Visit Description	Month 0 (Vax 1)	Month 1 (Vax 2)	Month 2	Month 6 (Vax 3)	Month 7	Month 12		End of Study	
Visit Window (Days)	1	28-42 Days After Visit 1	28-42 Days After Visit 2	140-168 Days After Visit 2	28-42 Days After Visit 4	165-195 Days After Visit 4	Every 280-392 Days After Visit 5 ^a	Not Applicable	
Subject completes e-diary	X	X		X					
Review e-diary data		←				→			

Abbreviations: CDI = *Clostridium difficile* infection; e-diary = electronic diary; Vax = vaccination; → = ongoing/continuous event.

- a. Following approval of protocol amendment 3, subjects already enrolled in the study should have an annual retention visit arranged at the earliest opportunity, and then every 280 to 392 days thereafter.
- b. Prior to vaccination.
- c. At the first annual retention visit only or potential CDI visit, whichever occurs first.
- d. Prior to vaccination, if at a vaccination visit.
- e. Optimally within 48 hours of the third unformed stool (Bristol stool chart types 5-7).
- f. Any AEs occurring up to 48 hours after each blood draw must be recorded.
- g. Visit is intended to be conducted by telephone but, if desired, may be conducted in person.

3. ENDPOINTS AND BASELINE VARIABLES: DEFINITIONS AND CONVENTIONS

3.1. Primary Endpoints

3.1.1. Primary Efficacy Endpoints

- First primary CDI incidence, as defined by case definition 1 ([Section 3.4.1](#)), per 1000 person-years of follow-up, assessed during up to 2 time periods (each analysis will be performed only if the preceding one was successful).
 - After receipt of the third dose of investigational product onwards.
 - After receipt of the second dose of investigational product onwards.

3.1.2. Primary Safety Endpoints

- Local reactions (pain, erythema, induration), as self-reported on electronic diaries (e-diaries) for up to 7 days following each dose of investigational product.
- Systemic events (fever, vomiting, headache, fatigue, new or worsening muscle pain, new or worsening joint pain), as self-reported on e-diaries for up to 7 days following each dose of investigational product.
- Nonserious AEs from signing of the informed consent document (ICD) to 1 month after receipt of the third dose of investigational product.
- SAEs from signing of the ICD to 6 months after receipt of the third dose of investigational product.

3.2. Secondary Endpoints

3.2.1. Secondary Efficacy Endpoints

The following endpoints are numbered to denote the order of evaluation.

- For the 3-dose family:
 1. The CDI incidence per 1000 person-years of follow-up, assessed after receipt of the third dose of investigational product onwards, of all CDI cases according to case definitions 1 and 2 ([Section 3.4.1](#) and [Section 3.4.2](#)).
 2. (a) Mean time to resolution of diarrhea in first primary episodes of CDI (case definition 1, [Section 3.4.1](#)).
 - (b) Proportion of subjects experiencing a first primary episode of CDI (case definition 1, [Section 3.4.1](#)) who have a non-protocol-related medically attended visit during the CDI episode.

3. CDI incidence per 1000 person-years of follow-up, assessed after receipt of the third dose of investigational product onwards, of recurrent CDI cases (see case definition 2, [Section 3.4.2](#)).

For the 3-dose family, each analysis will be performed only if the preceding analysis resulted in a statistically significant vaccine effect.

For the 2-dose family: subjects who received at least 2 doses of vaccine:

1. CDI incidence per 1000 person-years of follow-up, assessed after receipt of the second dose of investigational product onwards of all CDI cases according to case definitions 1 and 2 ([Section 3.4.1](#) and [Section 3.4.2](#)).
2. CDI incidence per 1000 person-years of follow-up, assessed after receipt of the second dose of investigational product onwards of recurrent CDI cases according to case definition 2 ([Section 3.4.2](#)).

For the 2-dose family: subjects who received only 2 doses of vaccine:

3. (a) The incidence of a first primary episode of CDI (see case definition 1, [Section 3.4.1](#)), assessed after receipt of the second dose but before the third dose of investigational product.

(b) The incidence of recurrent CDI (case definition 2, [Section 3.4.2](#)), assessed after receipt of the second dose but before the third dose of investigational product.

For the 2-dose family, each analysis will be performed only if the preceding analysis resulted in a statistically significant vaccine effect.

CCI [REDACTED]

CCI [REDACTED]	[REDACTED]
[REDACTED]	[REDACTED]
[REDACTED]	[REDACTED]
[REDACTED]	[REDACTED]

CCI [REDACTED]	[REDACTED]
[REDACTED] [REDACTED] [REDACTED]	[REDACTED]
[REDACTED] [REDACTED]	[REDACTED] [REDACTED] [REDACTED]
[REDACTED] [REDACTED]	[REDACTED]
[REDACTED] [REDACTED] [REDACTED] [REDACTED]	[REDACTED] [REDACTED] [REDACTED]

CCI [REDACTED]	[REDACTED]
[REDACTED]	[REDACTED]
[REDACTED]	[REDACTED]
[REDACTED]	[REDACTED]
CCI [REDACTED]	[REDACTED]
CCI [REDACTED]	[REDACTED]
[REDACTED]	[REDACTED]

3.4. CDI Case Definitions

For all definitions, an episode will be considered to have resolved once there have been at least 2 days without passage of 3 or more unformed stools (Bristol stool chart types 5-7) and there is no further need for antibiotic treatment for CDI.

For the purposes of analyses based upon case definitions 1 and 2 (described below), all collected stool samples will be tested at the central laboratory; however, only results from valid samples (ie, samples were from subjects who fulfill the clinical aspects of the case definition, and samples were successfully transported and stored within the required time period) will be included in the main analyses.

3.4.1. Definition 1 – Primary Episode

A primary episode of CDI (ie, no previous CDI onset in the prior 8 weeks) is defined as either:

- Presence of diarrhea, defined as passage of 3 or more unformed stools (Bristol stool chart types 5-7) in 24 or fewer consecutive hours; and
- Stool sample that is positive for the toxin B gene (via PCR) and positive for toxin A and/or toxin B, as measured in the central laboratory.

or:

- Pseudomembranous colitis diagnosed at colonoscopy, at surgery, or histopathologically; and corresponding stool sample that is positive for toxin B gene (via PCR) as measured in the central laboratory.

3.4.2. Definition 2 – Recurrent Episode

An episode of CDI that occurs 8 weeks or less after the onset of a previous CDI episode (provided the symptoms of the previous episode had resolved), defined as either:

- Presence of diarrhea, defined as passage of 3 or more unformed stools (Bristol stool chart types 5-7) in 24 or fewer consecutive hours; and
- Stool sample that is positive for the toxin B gene (via PCR) and positive for toxin A and/or toxin B, as measured in the central laboratory.

or:

- Pseudomembranous colitis diagnosed at colonoscopy, at surgery, or histopathologically; and corresponding stool sample that is positive for toxin B gene (via PCR) as measured in the central laboratory.

CCI [REDACTED]
[REDACTED]

- [REDACTED]
- [REDACTED]

CCI [REDACTED]
[REDACTED]

- [REDACTED]
- [REDACTED]

CCI [REDACTED]
[REDACTED]

CCI [REDACTED]

CCI [REDACTED]

CCI [REDACTED]

3.5. Other Endpoints

3.5.1. All-Cause Death, Diarrhea

Deaths will be recorded for the entire study duration. Death is defined as any subject who died during the active study. All-cause death includes deaths for any reason.

Diarrhea will be captured in the case report form (CRF) from the time of signing the ICD to the date the subject completes or withdraws from the study.

3.6. Baseline Variables

Day 1 is defined as the day of vaccination (Visit 1, Month 0) and also the start of when local reactions and systemic events are to be reported in the e-diary.

3.7. Safety Endpoints

3.7.1. Adverse Events

The time period for actively eliciting and collecting AEs and SAEs for each subject begins from the time the subjects provides informed consent, through and including the 1-month follow-up visit (Visit 5) after Vaccination 3. The collection of SAEs continues throughout the follow-up phase through 6 months after Vaccination 3. Additionally, any AEs occurring up to 48 hours after each blood draw (Visit 5) and at the time of a potential CDI case will be reported.

All events are collected on the CRF and will be categorized according to the current version (at the time of reporting) of the Medical Dictionary for Regulatory Activities (MedDRA).

A 3-tier approach will be used to summarize AEs. Under this approach, AEs are classified into 1 of 3 tiers. Different analyses will be performed for different tiers (see [Section 5.2.1.2](#)).

Tier 1 events: These are prespecified events of clinical importance and, if any, are maintained in a list in the product's Safety Review Plan.

Tier 2 events: These are events that are not tier 1 but are "common." A MedDRA preferred term is defined as a tier 2 event if its incidence is $\geq 1.0\%$ in any vaccine group.

Tier 3 events: These are events that are neither tier 1 nor tier 2 events.

AEs will be captured and reported in accordance with Pfizer reporting standards.

3.7.2. Reactogenicity Data

The reactogenicity data collected in the study e-diary will include local reactions (erythema/redness, induration/swelling, and pain at the injection site) and systemic events (fever, vomiting, headache, fatigue, new or worsening muscle pain, and new or worsening joint pain).

The e-diary will record reactogenicity data from Day 1 to Day 7 starting on the day of each vaccination, following investigational product administration.

3.7.2.1. Local Reactions Endpoints

Local Reactions: Presence or Absence

The presence of redness or swelling is to be recorded in the e-diary as “Yes” or “No.” If redness or swelling is present, then a second question is to appear requesting the size of the affected area; otherwise, no question is to appear. A measuring device with a scale ranging from 1 to 21 is to be used to measure the largest diameter in whole-number increments. Measurements are to be rounded up to the nearest whole number. If the area is larger than the measuring device can measure, “21+” is to be selected. Measuring device units are converted to centimeters according to 1 measuring device unit = 0.5 centimeters.

The presence of redness and swelling is defined according to the following scale:

= ., if missing

= No, if no or minimal redness or swelling is present, <2.5 cm (<5 measuring device units)

= Yes, if redness or swelling is ≥ 2.5 cm (≥ 5 measuring device units)

These categories (., No, Yes) will be used for derivation of the variables below. For the data summary of the presence (Yes or No) of a local reaction, the following variables are required:

█ [REDACTED]

- Presence of each local reaction on any day (Day 1 to Day 7) after each vaccination and after any vaccination.

█ [REDACTED]

- Presence of any local reaction on any day (Day 1 to Day 7) after each vaccination and after any vaccination.

The derivation of CCI [REDACTED] “any day” variables is given in [Table 5](#).

Table 5. Derived Variables for Each Local Reaction

Variable	Yes (1)	No (0)	Missing (.)
CCI			
Any day (Days 1-7)	Subject reports the reaction as “Yes” on any day (Day 1-7).	Subject reports the reaction as “No” on all 7 days or as a combination of “No” and missing on all 7 days.	Subject does not report on the reaction on all 7 days.

For any local reaction on any day, a similar rule applies as specified in Table 6.

Table 6. Derived Variables for Any Local Reaction

Variable	Yes (1)	No (0)	Missing (.)
CCI			
Any day (Days 1-7)	Subject reports any reaction as “Yes” on any day (Days 1-7).	Subject reports all reactions as “No” on all 7 days or as a combination of “No” and missing on all 7 days.	Subject does not report on any of the reactions (or reports a combination of “No” and missing) on any of the 7 days.

Maximum Severity for Local Reactions

Erythema/redness and induration/swelling are measured and recorded in measuring device units (range: 1-21+) and then categorized as absent, mild, moderate, or severe based on the grading scale in Table 7. Pain at the injection site will be assessed by the subjects as mild, moderate, or severe according to the grading scale in Table 7.

Table 7. Local Reaction Grading Scale

	Mild (Grade 1)	Moderate (Grade 2)	Severe (Grade 3)	Potentially Life Threatening (Grade 4)
Pain	Does not interfere with activity	Interferes with activity	Prevents daily activity	Emergency room visit or hospitalization for severe pain
Erythema/Redness	2.5 cm to 5.0 cm (5 to 10 measuring device units)	>5.0 cm to 10.0 cm (11 to 20 measuring device units)	>10 cm (≥21 measuring device units)	Necrosis or exfoliative dermatitis
Induration/Swelling	2.5 cm to 5.0 cm (5 to 10 measuring device units)	>5.0 cm to 10.0 cm (11 to 20 measuring device units)	>10 cm (≥21 measuring device units)	Necrosis

Only an investigator or medically qualified person is able to classify a subject's local reaction as Grade 4. Grade 4 could also be determined if a reaction is reported as an SAE.

The maximum severity (highest grading) of each local reaction within 7 days after each vaccination will be derived. The maximum severity will be derived as follows:

- = ., if values are missing for all days (Days 1-7);
- = 0, if the subject reports all reactions as "No" or a combination of missing and "No" for all days (Days 1-7);
- = *highest grade* (maximum severity) within 7 days after vaccination, if the answer is not "No" for at least 1 day.

Duration of Each Local Reaction

For subjects experiencing any local reactions (or those with a derived reaction as described in Table 7), the maximum duration (last day of reaction – first day of reaction + 1) will be derived for each study vaccination. Resolution of the event is the last day on which the event is recorded in the e-diary or the date the event ends if it is unresolved during the subject diary-recording period (end date collected on the CRF). If there is no known end date, the duration will be considered unknown and set to missing. However, if an event is ongoing at the time of a subsequent vaccination, the end date/day for the ongoing event would be the date/day that the next vaccine is administered, which will be used for the duration computation. Subjects with no reported reaction have no duration.

Onset of Each Local Reaction

The onset day of each local reaction and any local reaction will be derived.

The onset day for each local reaction is the first day the subject reports the local reaction, even if the reaction later becomes more severe. The onset day for any local reaction will be the first day of any of the 3 local reactions, regardless of severity. Onset day will be missing for subjects without the indicated local reaction.

In summary, the following variables will be derived for local reactions:

1. Each local reaction on CCI any day (Days 1-7) after each vaccination and after any vaccination.
2. Any local reaction on CCI any day (Days 1-7) after each vaccination and after any vaccination.
3. Maximum severity of each local reaction on "any day (Days 1-7)" after each vaccination and after any vaccination.
4. Maximum duration of each local reaction after each vaccination.

5. Onset day of each local reaction after each vaccination.
6. Onset day of any local reaction after each vaccination.

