5.3.1.1. Reactogenicity Data

For derived variables based on reactogenicity data, if any day of the 7-day e-diary is available, the “any day (Days 1-7)” data will be considered as nonmissing. Subjects are excluded from the analysis if they do not receive the particular dose or the safety data are missing on all days within the interval.

The reactogenicity data are collected through the e-diary, which does not allow subjects to skip the question. Therefore, for a specific day, as long as the e-diary data are transferred for that day, all of the reactogenicity data for the subject on that day are nonmissing. The e-diary transmission and completion status will be summarized per [Section 3.8.1](#). The e-diary completion summary will provide the missing data information on the reactogenicity data.

Based on data from available studies, the missing data on reactogenicity are minimal, which is consistent with Li et al (2011).⁸ No sensitivity analysis is planned for reactogenicity data.

[figure not shown]

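### SAP Table 6 codes one diary pattern (some 'No' days, some missing days, no 'Yes') as both 'No' and 'Missing' for any local reaction; the 'Missing' cell contradicts the rest of the SAP

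*SAP*

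**What the plan says.** SAP 3.7.2.1 derives two sets of any-day variables from the seven-day e-diary.

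- **Table 5, each local reaction.** A mix of 'No' and missing days is coded 'No'. The variable is missing only if "Subject does not report on the reaction on all 7 days".
- **Table 6, any local reaction.** The text leads into it with "For any local reaction on any day, a similar rule applies as specified in Table 6". Its 'No (0)' cell reads "Subject reports all reactions as “No” on all 7 days or as a combination of “No” and missing on all 7 days". Its 'Missing (.)' cell, in the same row, begins "Subject does not report on any of the reactions (or reports a combination of" and completes the parenthesis with 'No' and missing, on any of the seven days.

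Two other rules cover the same diary data.

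- **Maximum severity (SAP 3.7.2.1).** The value is missing "if values are missing for all days (Days 1-7"), and it is 0 if every answer is 'No' "or a combination of missing and" 'No'.
- **Missing reactogenicity data (SAP 5.3.1.1).** The any-day variable counts as nonmissing "if any day of the 7-day e-diary is available". On the denominator: "Subjects are excluded from the analysis if they do not receive the particular dose or the safety data are missing on all days" in the interval.

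SAP 3.7.2.2 derives the systemic-event variables in a similar way to the local-reaction ones. SAP 6.1.2.1 reports the any-reaction and any-event percentages by vaccine group with 95% Clopper-Pearson intervals.

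**The concern.** A derivation table should give each data pattern exactly one code, and this row does not. The two codes also have different consequences. Coded 'No', a subject with a partial diary and no reported reaction stays in the denominator. Coded 'Missing', the subject drops out. A subject who missed the same number of days but recorded one 'Yes' is kept under either rule, so the 'Missing' code removes people only from the non-reactor side.

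At stake is the composite any-local-reaction percentage, reported among the primary safety summaries, and any systemic event if the wording is carried over. Under the 'Missing' cell the composite would have a smaller denominator than pain, redness and swelling in the same table. A subject could be 'No' for all three reactions and grade 0 for severity, yet missing for any reaction.

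**Working it through.** The documents give neither a reaction rate nor a missed-day rate, so there is no stated figure to reproduce. The check has two parts: how far the two cells overlap, and what the choice between them does to the percentage.

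**1. Overlap.** SAP 5.3.1.1 says that the diary does not allow a question to be skipped, so local-reaction data go missing by whole days. Each day is then one of three states: at least one 'Yes', all 'No', or missing.

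- All seven-day patterns: 3^7 = 2,187.
- Patterns with no 'Yes': 2^7 = 128, so 2,187 − 128 = 2,059 patterns are coded 'Yes'.
- Patterns meeting the 'No' cell: 128 less the all-missing pattern = 127.
- Patterns meeting the 'Missing' cell: 128 less the all-'No' pattern = 127.
- Patterns meeting both: 128 − 2 = 126.

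Among patterns without a 'Yes', only all-'No' and all-missing have a single code. None of the 126 overlapping patterns contains a 'Yes'. If 'Missing' is limited to all seven days missing, as in Table 5, the overlap is 0 and no pattern is left uncoded.

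Partial diaries are foreseen: SAP 3.8.1 defines completion categories for 6, 4 or 5, 2 or 3, and 0 to 1 complete days out of seven.

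**2. Effect on the percentage.** Let p be the rate with partial diaries coded 'No', as 5.3.1.1 requires. Let q be the share of subjects with no reported reaction, and at least one diary day, who have at least one missing day. Under the 'Missing' cell the rate becomes

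p / [p + (1 − p)(1 − q)],

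which exceeds p whenever 0 < p < 1 and q > 0.

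Example with p = 30% in 1,000 subjects, so 300 with and 700 without a reported reaction. At q = 10%, 70 are dropped and the rate is 300/930 = 32.3%. At q = 1%, 7 are dropped: 300/993 = 30.2%. At q = 20%, 140 are dropped: 300/860 = 34.9%.

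Both p and q below are assumed:

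| p under 5.3.1.1 | q = 1% | q = 5% | q = 10% | q = 20% |
|---|---|---|---|---|
| 10% | 10.1% | 10.5% | 11.0% | 12.2% |
| 30% | 30.2% | 31.1% | 32.3% | 34.9% |
| 60% | 60.2% | 61.2% | 62.5% | 65.2% |

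The rise is about 0.1 to 0.2 percentage points at q = 1% and 2.2 to 5.2 points at q = 20%.

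**The case against.** **The SAP already answers the question elsewhere.** Section 5.3.1.1 is the missing-data section and addresses this variable and this denominator. Protocol 9.4 likewise takes the reactogenicity population to be subjects who received the dose and have e-diary information. With Table 5, the severity rule and Table 6's own 'No' cell, everything points against one parenthetical. This stands as a guide to intent, and it makes the higher percentage conditional on a programmer following the outlying cell. It does not remove the contradiction: the SAP states no order of precedence, and Table 6 is the variable-specific rule.

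**The parenthetical may mean a mix across the three reactions within one day.** Table 6 has that extra dimension and Table 5 does not. But the wording is not limited to a single day, and with a diary that cannot be skipped the clause would then be empty for local reactions. For systemic events it need not be empty: SAP 3.7.2.3 excludes temperatures below 35.0°C or above 42.0°C, so fever can be missing on a day when the other events are 'No'. The row above in Table 6 is redacted and gives no help either way.

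**Missing data are expected to be minimal.** SAP 5.3.1.1 says so, without a percentage. This stands, and it makes the low end of the table the more likely region.

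Three stronger readings are tempting and are not supported.

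- A reader might infer that the primary safety results are inflated. The endpoint names pain, erythema and induration, and each is derived by Table 5, which is unambiguous. Only the composite is exposed, and only if the 'Missing' cell is used.
- A reader might infer that reaction-free subjects are dropped and the true rate is overstated. The dropped subjects have no *reported* reaction, and a missed day can hide one. The 'No' code may itself understate the true rate. The figures compare two coding rules; they do not measure distance from the truth.
- A reader might infer a distorted between-arm difference. The plan summarizes reactogenicity descriptively by group. Risk differences are specified only for tier 1 and tier 2 adverse events.

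**Conclusion.** Wrong as written. The any-day row of Table 6 gives two codes to any partial diary without a 'Yes', and its 'Missing' cell contradicts its own 'No' cell, Table 5, the maximum-severity rule and SAP 5.3.1.1.

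The consequence is conditional and probably small. If the 'Missing' cell is programmed, the any-local-reaction percentage is higher than under 5.3.1.1 and rests on a different denominator from the individual reactions; any systemic event follows by analogy. The direction follows from the algebra. The size rests on assumed values of p and q, and with missing data described as minimal it may be a fraction of a percentage point. Individual reactions, maximum severity and all efficacy analyses are unaffected.

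**What to change.** In the any-day row of Table 6, delete the parenthetical from the 'Missing (.)' cell and leave the rest of the cell as it is. The variable is then missing only when none of the reactions was reported on any of the seven days, which matches Table 5 and SAP 5.3.1.1. Add a line to SAP 3.7.2.2 applying the same rule to any systemic event.

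The cost is one table cell and one sentence in the SAP, plus a check that the programming specification follows 5.3.1.1. No data collection, hypothesis test or sample size changes.
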